4.8.2 Sample Size

A total of 90 subjects per arm will provide 80% power to detect a [REDACTED] reduction in infarct size between MEDI6012 [REDACTED] group and combined placebo group ([REDACTED] placebo groups), and between MEDI6012 [REDACTED] group and combined placebo group with one-sided alpha 0.05 assuming a coefficient of variation of [REDACTED]. A total of 180 subjects per arm is

required as a █% rate of exclusion from the primary efficacy analysis population is expected due to █ in the infarct-related artery on initial angiography and other reasons for subsequent exclusion or drop-out (Botker et al, 2010; Hausenloy et al, 2013). A █ reduction in infarct size is thought to be clinically significant, assuming it would equate to an approximate █% absolute reduction in infarct size in a future trial that enrolls subjects with large infarcts. A █% absolute reduction in infarct size is associated with a █% relative risk reduction in heart failure and mortality. With this same sample size, the power to detect a █% absolute difference in EF between each MEDI6012 group and combined placebo group with █ alpha █ is > █% assuming standard deviation █%. For the secondary endpoint of non-calcified coronary plaque regression/progression, there will be > █% power to detect a █ mm³ change in NCPV from index CTA to the 10-12 week CTA between MEDI6012 group and placebo group with █ assuming a common standard deviation of █ mm³ and █% drop-out. It is estimated that the study will involve approximately 43 sites in approximately 10 countries.

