9.2 Protocol Amendment 5, 26Jul2019

Text revisions resulting from this amendment are incorporated into the body of Protocol Amendment 5. All changes made to the body of the protocol have been reflected in the Protocol Synopsis and minor copyediting issues were addressed.

Changes to the protocol considered substantial are summarized below:

- 1 Section 3.1.1 (Overview), Figure 3 (Overall Study Schema), 3.1.2 (Treatment Regimen), 4.1.1 (Number of Subjects), 4.6.1 (Methods for Assigning Treatment Groups), 4.8.1 (General Considerations), 4.8.2 (Sample Size), and 4.8.8 (Interim Analysis): the approximate number of subjects was changed from at least 414 to approximately 540; total numbers per cohort, sample size calculation and second interim analysis were updated to reflect this. Sample size change was implemented to reflect the observed coefficient of variation of blinded data relative to the expected in the statistical assumption. The alpha threshold was amended to be a one-sided alpha of 0.05 to reflect

the one-sided hypothesis testing (superiority of MEDI6012) for this Phase 2b program designed to inform future drug development.

Changes to the protocol considered non-substantial are summarized below:

- 2 Title Page: medical monitor changed to [REDACTED]
- 3 Section 3.1.1 (Overview) and 4.8.2 (Sample Size): number of study sites updated from 40 to 43.
- 4 Table 5 (Exploratory Objectives and Associated Endpoints), and Section 3.2.3.4 (Rationale for Exploratory Endpoints): [REDACTED]
[REDACTED]
- 5 Section 4.1.4 (Additional Study Procedure Requirements): under Coronary CTA, the fifth requirement was revised to read, “No contraindication to heart rate lowering using betablockers to allow for high quality, low-radiation dose CTA (per-protocol). Please note, if heart rate is well-controlled allowing for a high quality, low radiation CTA without betablocker, then a contraindication to betablocker does not exclude the subject from coronary CTA”. The text was revised to clarify that if betablockers are contraindicated, subject could still undergo CTA if their heart rate is low enough to assure a low radiation dose can be achieved. Nitroglycerin contraindication was removed from the list of requirements since subjects could undergo CTA without nitroglycerin administration.
- 6 Section 4.8.1.1 (Analysis Populations): descriptions of analysis populations updated to reflect the statistical analysis plan.

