2.4 Sample Size

3 STATISTICAL METHODS

3.1 General Considerations

An initial database lock for the purpose of clinical study analysis and reporting will be performed when the last randomized subject completes the Day 70 to 84 visit or is discontinued prior to that visit; if no subjects are ongoing in the Extended Follow-up period, then this database lock will be considered the final database lock for the study.

If subjects are ongoing in the Extended Follow-up period, a second database lock will occur after all subjects who entered the Extended Follow-up period have completed their Week 25,

39, or 52 visits as needed or are discontinued prior to these visits, and this will be considered the final database lock. If the last Extended Follow-up visit occurs before the last Day 70 to 84 visit on the study, the second database lock will not be needed.

The study will be unblinded to the sponsor at the time of initial database lock. The site, subjects, and local CRO personnel will remain blinded to treatment assignment until the final database lock is declared.

Safety data will be generated for the Extended Follow-up period and summarized as an addendum to the clinical study report.

Data will be provided in listings sorted by treatment group and subject number. Tabular summaries will be presented by treatment group with placebo group combined when appropriate. Categorical data will be summarized by the number and percentage of subjects in each category. Continuous variables will be summarized by descriptive statistics. Baseline values will be defined as the last valid assessment prior to the first administration of investigational product on Day 1 unless data are missing, in which case, baseline will be defined as the last value prior to dosing. All statistical tests will be one-sided (based on protocol amendment) at an alpha = 0.05 significance level unless stated otherwise.

Confidence intervals will be one-sided (based on protocol amendment) and nominal p-values will be reported when appropriate.

Data analyses will be conducted using the SAS® System Version 9.3 or higher (SAS Institute Inc., Cary, NC) unless otherwise specified.

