4 INTERIM ANALYSIS

Two interim analyses are planned. The objectives of the first interim analysis will be to assess futility and potentially to drop a dose regimen. The analysis, which will be conducted after 30% of the Primary Efficacy Analysis Population (assumed 40% rate of exclusion from the primary efficacy analysis population is expected due to TFG 2 or 3 flow in the infarct-related artery on initial angiography and other reasons for subsequent exclusion or drop-out) based on the original sample size ($N = 74$) is enrolled, will require that $> 50\%$ of subjects ($N > 37$) have acute anterior STEMI and have completed their final study visit. The first interim analysis will be conducted through the Independent Data Monitoring Committee (IDMC). The second interim analysis is planned to accelerate decision on future development options for MEDI6012 and will be performed once 60% of the Primary Efficacy Analysis Population (assumed 50% rate of exclusion from the primary efficacy analysis population is expected due to TFG 2 or 3 flow in the infarct-related artery on initial angiography and other reasons for subsequent exclusion or drop-out) based on the revised sample size ($N = 162$) is enrolled and will require that $> 50\%$ of subjects ($N > 81$) have acute anterior STEMI and have completed their final study visit. Details of the second interim analyses will be specified in the unblinding plan. The sponsor and Principal Investigator will monitor the statistical assumptions in a blinded fashion and schedule the interim analyses accordingly.

The assessment of futility will be based on predictive power, which is conditional power averaged over the distribution of the observed treatment effect at the time of interim analysis. The futility analysis will include all available data at the time of the interim data cut.

The predictive power based on the empirical trend observed at the interim analysis will be calculated by

$$\text{predictive power } pp = \Phi\left(\frac{z_\tau - z_{1-\alpha/2}\sqrt{\tau}}{\sqrt{1-\tau}}\right)$$

τ is the information fraction at the interim analysis, z_τ is the observed value of the test statistic at the interim, α is the two-sided significance level at the final analysis based on the original protocol, and Φ is the standardized normal density function.

Each MEDI6012 dose regimen will be compared to the combined placebo group (pooled over dose regimens).

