The study may be declared as “futile” if for both the 2-dose and the [redacted] regimens the calculated predictive power is < 20% for

- infarct size in the Primary Efficacy Analysis Population; AND
- ejection fraction in the Primary Efficacy Analysis Population; AND
- infarct size in the Efficacy Analysis Population - TIMI 0-3; AND
- ejection fraction in the Efficacy Analysis Population - TIMI 0-3.

The [redacted] regimen may be dropped if the calculated predictive power is < 20% for

- infarct size in Primary Efficacy Analysis Population; AND
- ejection fraction in Primary Efficacy Analysis Population; AND
- infarct size in Efficacy Analysis Population – TIMI 0-3; AND
- ejection fraction in Efficacy Analysis Population – TIMI 0-3.

For illustration purposes, Figure 4.1 provides the estimated predictive power when the observed infarct size reduction varies from -20 to 50% in the Primary Efficacy Analysis Population. The 20% predictive power translates into an infarct size reduction of approximately 7%. A value of 50% will result in 18% infarct size reduction, which is the minimally detectable treatment effect for this study. Figure 4.2 provides the estimated predictive power when the observed ejection fraction increase varies from a -5 to 10% in the

Primary Efficacy Analysis Population. Calculated predictive power will be based on observed data.

Figure 4.1

Predictive power against observed interim relative infarct size reduction when 30% of the Primary Efficacy Analysis Population is enrolled and complete their final study visit

[figure not shown]
[figure not shown]

Figure 4.2

Predictive power against observed interim ejection fraction increase when 30% of the Primary Efficacy Analysis Population is enrolled and complete their final study visit

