3.0	03Dec2020	
Add more details of interim analysis (e.g., predictive power).
 
Add reference of formula of predictive power.
 
Add data handling approach of zero infarct size.
 
Align with protocol amendment with updated numbers related to sample size inflation and changes from two-sided to one-sided significance/alpha.
 
Align with protocol amendment for potential 2 DBLs and extended follow-up period data report.
 
Add statistical checking for the data distribution and applicable statistical testing based on distribution assumption to ensure the statistical appropriateness
 
Add COVID-19 subsection and analysis
 
Remove subgroup of statin therapy intensity
 
Remove ECG language which is not applicable
 
Align with protocol amendment with updated CV endpoints

Certificate Of Completion

Envelope Id: 6479FDB22D46424AA9DD72933481FD02 Status: Completed

Subject: Please DocuSign: D5780C00007 Statistical Analysis Plan V3.0.docx, D5780C00007_Statistical Analy...

Source Envelope:

Document Pages: 27 Signatures: 4

Certificate Pages: 3 Initials: 0

AutoNav: Enabled

EnvelopeD Stamping: Disabled

Time Zone: (UTC+01:00) Brussels, Copenhagen, Madrid, Paris

Envelope Originator:

[name]
[name]

IP Address: 5

Record Tracking

Status: Original

Holder:

Location: DocuSign

04-Dec-20 | 14:15

Signer Events

Signature

Timestamp

AstraZeneca

Security Level: Email, Account Authentication
(None)

Signature Adoption: Pre-selected Style
Using IP Address:

Sent: 04-Dec-20 | 14:27

Viewed: 04-Dec-20 | 14:52

Signed: 04-Dec-20 | 14:52

Electronic Record and Signature Disclosure:

Accepted: 07-Feb-20 | 21:00

ID: ce7ecddc-69d8-439f-af15-78b7ffd4c7a3

Dr

AstraZeneca

Security Level: Email, Account Authentication
(None)

Signature Adoption: Pre-selected Style
Using IP Address:

Sent: 04-Dec-20 | 14:27

Viewed: 04-Dec-20 | 14:37

Signed: 04-Dec-20 | 14:37

Electronic Record and Signature Disclosure:

Accepted: 21-Feb-20 | 06:22

ID: 60f39848-df04-4f4f-b38a-07cce0c831a2

Security Level: Email, Account Authentication
(None)

Signature Adoption: Pre-selected Style
Using IP Address:

Sent: 04-Dec-20 | 14:27

Resent: 08-Dec-20 | 01:22

Viewed: 08-Dec-20 | 05:43

Signed: 08-Dec-20 | 05:44

Electronic Record and Signature Disclosure:

Accepted: 08-Dec-20 | 05:43

ID: 91f643b6-1542-4b52-958b-71097b9e9e04

SENIOR PRINCIPAL STATISTICIAN

AstraZeneca

Security Level: Email, Account Authentication
(None)

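### The futility predictive power uses the original protocol's two-sided critical value, while the final test in the same SAP is one-sided 0.05, so a nominal 20% is about 26% for the planned analysis

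*SAP*

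**What the plan says.** SAP Section 4 bases futility at the first interim on predictive power, pp = Φ((z_τ − z(1−α/2)√τ)/√(1−τ)). Here τ is the information fraction, z_τ is the interim test statistic, and α "is the two-sided significance level at the final analysis based on the original protocol". The same passage says that Φ "is the standardized normal density function".

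A regimen may be dropped if predictive power is below 20% for infarct size and for ejection fraction, in both the Primary Efficacy Analysis Population and the TIMI 0-3 population. The study may be called futile if this holds for both regimens. Two illustrations for infarct size follow: "The 20% predictive power translates into an infarct size reduction of approximately 7" per cent, and "A value of 50% will result in 18% infarct size reduction, which is the minimally detectable treatment effect for this study".

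The final test is set elsewhere:
- SAP Section 3.1: "All statistical tests will be one-sided (based on protocol amendment) at an alpha = 0.05 significance level unless stated otherwise".
- Protocol Section 4.8.2 sizes the trial for each regimen against the "combined placebo group with one-sided alpha 0.05 assuming a coefficient of variation of" a redacted value.
- Protocol Section 9.2 (Amendment 5, 26Jul2019): "The alpha threshold was amended to be a one-sided alpha of 0.05". The same amendment raised the planned total from at least 414 to about 540.
- SAP Section 6, for version 3.0 (03Dec2020), lists added predictive-power detail and, in the same revision, alignment with the "changes from two-sided to one-sided significance/alpha".

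**The concern.** Predictive power answers one question: given the interim data, how likely is the final test to succeed? The critical value in the formula must therefore be that of the final test. SAP version 3.0 carries two: the original two-sided one in Section 4 and the one-sided 0.05 one in Section 3.1. If the first is the larger, the formula understates the chance of success, and a regimen can score below 20% when its predictive power for the test that will actually be run is above 20%.

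The illustrations add to this. The 18% figure is offered as the detectable effect of the study, with no note that it belongs to the superseded design. A monitoring committee reading Section 4 could take both figures as describing the current design.

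**Working it through.** **Inputs.** τ = 0.30 for the illustrations (captions of SAP Figures 4.1 and 4.2); 18% reduction at 50% predictive power and about 7% at 20% (SAP Section 4); log-scale two-sample t-test (SAP 3.4.1.3); z(0.20) = −0.842. Original evaluable number: 414 × 0.60 = 248.4, and 0.30 × 248.4 = 74.5, printed as 74. Revised evaluable number: 540 × 0.50 = 270.

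**1. Reproduce the SAP's figures.** For a given predictive power, z_τ = z_c√τ + z(pp)√(1−τ). With z_c = 1.960:
- 50%: z_τ = 1.960 × 0.5477 = 1.0735.
- 20%: z_τ = 1.0735 − 0.842 × 0.8367 = 0.369.
- The 18% figure fixes the interim standard error on the log scale: −ln(0.82)/1.0735 = 0.1985/1.0735 = 0.185.
- Predicted reduction at 20%: 1 − exp(−0.369 × 0.185) = 6.6%, which agrees with about 7%.

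**2. Which critical value do the figures imply?** Anchoring on 18% with z_c = 1.645 would put the 20% point at 4.2%, which does not match. Solving the 7%/18% pair for z_c gives 2.03, or 1.91 to 2.16 allowing for rounding. That range includes 1.96 and excludes 1.645. A two-sided 0.05 original level is thus an inference, but a well-supported one.

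**3. Score the SAP's 20% boundary against the one-sided 0.05 test.** With z_τ = 0.369 and τ = 0.30: Φ((0.369 − 1.645 × 0.5477)/0.8367) = Φ(−0.635) = 0.26. With τ = 74/270 = 0.274 the result is 0.28.

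**4. Where the 20% boundary falls for the one-sided 0.05 test.**
- τ = 0.30, standard error 0.185: z_τ = 0.901 − 0.704 = 0.197, a 3.6% reduction.
- τ = 0.274, same standard error: z_τ = 0.144, a 2.6% reduction.
- τ = 0.274, SD 10% to 30% larger (assumption, since the coefficient of variation is redacted): 2.9% to 3.4%.

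The boundary is therefore roughly 3-4% under each of these assumptions.

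**5. The 50% point.** With 1.645 and the old standard error it is 15.3% at τ = 0.30 and 14.7% at τ = 0.274. With an SD 10% to 30% larger and τ = 0.274 it is 16.1% to 18.7%. The documents do not say which applies.

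**6. Effect on one criterion (τ = 0.30).** For a true effect with 80% power at one-sided 0.05, the interim mean of z is (1.645 + 0.842) × 0.5477 = 1.362.
- Probability of scoring below 20% as written: Φ(0.369 − 1.362) = 16.0%.
- With 1.645: Φ(0.197 − 1.362) = 12.2%.
- Under no effect: Φ(0.369) = 64.4% as written and Φ(0.197) = 57.8% with 1.645.

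The four-criterion rule fires less often than any single criterion. By how much depends on correlations that the documents do not give.

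**The case against.** The strongest reply is that the original-design basis is disclosed and may be deliberate. SAP Section 4 and Protocol Section 4.8.8 both tie the first interim to the original sample size and only the second to the revised one, and the Amendment 5 log names only the second interim as updated. If the first interim preceded Amendment 5, the formula matched the final test then in force, and substituting 1.645 now would misdescribe the rule applied. The DMC charter, which holds further detail, is not among the documents. This stands as a reason for a conditional fix. It does not remove the mismatch: version 3.0 describes the first interim in the future tense, postdates Amendment 5, added the predictive-power detail while adopting one-sided testing, and gives no date for the interim.

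The reply is also right that the consequences are limited. The rule says only that futility may be declared. The IDMC must first consider plaque and clinical outcome data, and the sponsor's review committee may be asked to consider continuing. Under Protocol Section 4.2.1.1 all new subjects already go to Cohort B, so by version 3.0 dropping Cohort A would not have changed enrolment.

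Three stronger readings are tempting but not supported:
- **That 7% and 18% are miscalculated.** They reproduce on the basis the SAP states, and they are offered as illustrations.
- **That 18% should read 15.3%.** This pairs the new α with a standard error from the old design, although Amendment 5 raised the sample size because of the observed coefficient of variation. If the target effect is unchanged and current power is 80% at one-sided 0.05, the smallest significant reduction is 17.1% for an original power of 80% (log effect 2.802 × 0.1013 = 0.284; × 1.645/2.487 = 0.188) and 19.5% for 90%. So 18% may still be about right.
- **That futility would be computed from a normal density.** A density cannot exceed 0.399, yet the SAP reports a 50% value, and the 7%/18% pair reproduces with the cumulative function. The word is a slip.

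Nor does the formula fix τ at 0.30. That value belongs to the trigger and the illustrative figures.

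**Conclusion.** The mismatch is real. As written, the quantity compared with 20% is not the probability of success at the one-sided 0.05 final analysis in the same SAP. At τ = 0.30 the nominal 20% threshold acts like about 26%, and the true 20% boundary is at roughly a 3-4% observed reduction instead of about 7%.

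These sizes rest on an original level of two-sided 0.05, inferred from the illustrations. The reductions also rest on a standard error back-solved from the 18% figure, with a range for the redacted coefficient of variation. The 7% and 18% figures are coherent for the original design but are not labelled as such. Whether 18% still holds under the amended design cannot be determined.

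The practical effect is modest. The rule leans slightly towards calling futility, is permissive and needs four criteria together, and type I error is not raised. Whether the first interim preceded Amendment 5 is not settled by the documents, and that decides which correction applies.

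**What to change.** In SAP Section 4:
- **For any futility assessment made under the amended design:** replace z(1−α/2) with z(1−α), one-sided α = 0.05. Take τ as evaluable subjects at the interim divided by the revised final evaluable number. Recompute the 20% and 50% illustrations and Figures 4.1 and 4.2 with the updated coefficient of variation.
- **If the first interim was completed before Amendment 5:** keep the formula, state the date of the interim and the original α, and label the formula and the 7% and 18% figures as original-design values.
- **In either case:** define Φ as the standard normal cumulative distribution function.

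The cost is one formula line, two illustrative numbers and two figures, or a few labelling sentences. The statistical price of the first option is that an ineffective regimen is stopped slightly less often.

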6 VERSION HISTORY

Version	Date	Summary of Changes	Reason for Change
1.0	04Jun2018	Initial document	Initial document
2.0 First Approv ed Version in e- TMF/V eeva Vault	01Jul2018	
Revised the section 3.2 Analysis Populations.
 
-Primary Efficacy Analysis population: Subjects who receive "2" or more doses of MEDI6012 will be placed to MEDI6012 group.
 
Subjects who receive "6" doses of [REDACTED]
 
Revised the section 3.4.1.5 Subgroup Analyses.
 
- Above vs below the median symptom onset-to-“device” time
 
Added section 3.6.4.2 Electrocardiogram
 
- Electrocardiogram will be summarized using descriptive statistics at end of the study by treatment group.
	
Incorporated team comments.
 
If Patient gets [REDACTED] of placebo and then 1 dose of MEDI6012 at end, we won't put in the MEDI arm when assessing efficacy. We modified the language for the clarification. Primary efficacy analysis population: Randomized subjects who receive at least [REDACTED] doses of investigational product with TFG 0 or 1 or initial angiography. Subjects who receive all placebo doses will be included in the placebo group; conversely, subjects who receive [REDACTED] doses of MEDI6012 will be placed to MEDI6012 group.
 
If Patient gets [REDACTED] doses of placebo and then 1 dose of MEDI6012 at end, we won't put in MEDI arm when assessing CTA analysis. We modified the language for the clarification. CTA Analysis

		
Population: Randomization subjects in [REDACTED] regimen who receive a full treatment course of investigation product. Subjects who receive all placebo doses will be included in the placebo group; conversely, subjects who receive [REDACTED] of MEDI6012 will be placed to MEDI6012 group.
 
Currently the eCRF database captures symptom onset time and device time. We changed balloon to device for subgroup analysis.
 
We added section 3.6.4.2 for Electrocardiogram.

3.0	03Dec2020	
Add more details of interim analysis (e.g., predictive power).
 
Add reference of formula of predictive power.
 
Add data handling approach of zero infarct size.
 
Align with protocol amendment with updated numbers related to sample size inflation and changes from two-sided to one-sided significance/alpha.
 
Align with protocol amendment for potential 2 DBLs and extended follow-up period data report.
 
Add statistical checking for the data distribution and applicable statistical testing based on distribution assumption to ensure the statistical appropriateness
 
Add COVID-19 subsection and analysis
 
Remove subgroup of statin therapy intensity
 
Remove ECG language which is not applicable
 
Align with protocol amendment with updated CV endpoints

Certificate Of Completion

Envelope Id: 6479FDB22D46424AA9DD72933481FD02 Status: Completed

Subject: Please DocuSign: D5780C00007 Statistical Analysis Plan V3.0.docx, D5780C00007_Statistical Analy...

Source Envelope:

Document Pages: 27 Signatures: 4

Certificate Pages: 3 Initials: 0

AutoNav: Enabled

EnvelopeD Stamping: Disabled

Time Zone: (UTC+01:00) Brussels, Copenhagen, Madrid, Paris

Envelope Originator:

[name]
[name]

IP Address: 5

Record Tracking

Status: Original

Holder:

Location: DocuSign

04-Dec-20 | 14:15

Signer Events

Signature

Timestamp

AstraZeneca

Security Level: Email, Account Authentication
(None)

Signature Adoption: Pre-selected Style
Using IP Address:

Sent: 04-Dec-20 | 14:27

Viewed: 04-Dec-20 | 14:52

Signed: 04-Dec-20 | 14:52

Electronic Record and Signature Disclosure:

Accepted: 07-Feb-20 | 21:00

ID: ce7ecddc-69d8-439f-af15-78b7ffd4c7a3

Dr

AstraZeneca

Security Level: Email, Account Authentication
(None)

Signature Adoption: Pre-selected Style
Using IP Address:

Sent: 04-Dec-20 | 14:27

Viewed: 04-Dec-20 | 14:37

Signed: 04-Dec-20 | 14:37

Electronic Record and Signature Disclosure:

Accepted: 21-Feb-20 | 06:22

ID: 60f39848-df04-4f4f-b38a-07cce0c831a2

Security Level: Email, Account Authentication
(None)

Signature Adoption: Pre-selected Style
Using IP Address:

Sent: 04-Dec-20 | 14:27

Resent: 08-Dec-20 | 01:22

Viewed: 08-Dec-20 | 05:43

Signed: 08-Dec-20 | 05:44

Electronic Record and Signature Disclosure:

Accepted: 08-Dec-20 | 05:43

ID: 91f643b6-1542-4b52-958b-71097b9e9e04

SENIOR PRINCIPAL STATISTICIAN

AstraZeneca

Security Level: Email, Account Authentication
(None)

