3.2 Rationale for Dose, Population, and Endpoints

3.2.1 Dose Rationale

Since this study will involve treating acute STEMI subjects in the acute setting, the aim is to increase [REDACTED]. The rate of [REDACTED] 1 increase with MEDI6012 are [REDACTED]. Therefore, on Day 1 a loading dose of MEDI6012 [REDACTED] or placebo will be administered to achieve a [REDACTED]. Based on PK modeling, [REDACTED] is expected to increase ~50% in 90 minutes and ~100% in 6 hours (assuming a mean [REDACTED] in acute STEMI patients). In addition, improved [REDACTED] L function is expected based on cholesterol efflux capacity data from study D5780C00002. A [REDACTED] dose of [REDACTED] of MEDI6012 or placebo will be administered 48 hours [REDACTED] following the [REDACTED] dose to maintain [REDACTED] during the acute and

sub-acute phases of MI. For the [REDACTED] regimen, dosing will be complete. For the [REDACTED] [REDACTED], subjects will receive 4 additional weekly [REDACTED] doses as an outpatient. A maintenance dose of [REDACTED] was selected to [REDACTED] at a level conferring benefit in epidemiology studies and at a level, predicted by PD/PK modeling from study D5780C00002 and D5780C00005, not to result in an appreciable accumulation of [REDACTED]. Increases in [REDACTED]

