4.1.2 Inclusion Criteria

Subjects must meet all of the following criteria:

- 1 Men and women without child-bearing potential (for definitions see Section [10.2](#)) aged 30-80 years of age who are capable and willing to provide informed consent.
- 2 Acute STEMI diagnosed by ST elevation (≥ 0.1 mV) in 2 contiguous leads
- 3 Planned for pPCI
- 4 Ischemic symptoms for ≤ 6 hours
- 5 Capable of completing study visits

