3.4.1.5 Subgroup Analyses

The primary endpoint of infarct size will be analyzed for the following subgroups. The first set of subgroups are based on baseline characteristics and time of treatment administration.

- Sex: male vs female

- Diabetic vs non-diabetic
- Smoker vs non-smoker
- Infarct location: anterior vs non-anterior
- TIMI Flow Grade 0 vs 1 vs 2 vs 3 pre-pPCI
- TIMI Flow Grade 0 or 1 vs 2 or 3 pre-pPCI
- Above vs below the median door-to-device time
- Above vs below the median symptom onset-to-device time
- Above vs below the median symptom onset-to-door time

The second set of subgroups, outlined in Table 3.2, are based on post-randomization outcomes and will not be used to make comparisons between treatment and placebo.

Table 3.2 Post-randomization Analysis Subgroups

Endpoint	Comparison Groups
Infarct size by culprit vessel location determined by baseline invasive coronary angiography	LAD vs Non-LAD LAD vs Left Circumflex Artery vs Right Coronary Artery
Infarct size by timing of drug administration	Investigational product administration before vs after pPCI Above vs below the median time between Dose 1 and pPCI
Infarct size by post-pPCI TIMI Flow Grade	TIMI Flow Grade 0 vs 1 vs 2 vs 3 post-pPCI TIMI Flow Grade 0 or 1 vs 2 or 3 post-pPCI

Infarct size by lipid and apolipoprotein levels	
Above vs. below the median HDL at baseline
 
Above vs. below the median HDL change from baseline
 
Above vs. below the median apoA1 at baseline
 
Above vs. below the median apoA1 change from baseline

Infarct size by cardiovascular event status	
Any CV event vs no CV event
 
HF Hospitalization vs No HF

LAD = left anterior descending artery; pPCI = primary percutaneous coronary intervention; CV = cardiovascular; HF = heart failure

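### In the readable SAP text, ischaemic-time intervals enter the subgroup analyses only as splits at the sample median, which discards about 36% of the information on a linear effect-by-time relation

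*SAP*

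**What the plan says.** SAP 3.4.1.5 gives two sets of subgroups for infarct size. The first set, described as resting on baseline characteristics and time of treatment administration, contains three intervals:

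- "Above vs below the median door-to-device time"
- "Above vs below the median symptom onset-to-device time"
- "Above vs below the median symptom onset-to-door time"

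SAP 3.4.2.4 lists the same three splits for every secondary endpoint. A fourth interval, "Above vs below the median time between Dose 1 and pPCI", is in the post-randomization table, which the SAP says will not be used to compare MEDI6012 with placebo.

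The version history (v2.0 entry) records: "Currently the eCRF database captures symptom onset time and device time. We changed balloon to device for subgroup analysis". That entry explains a change of wording from balloon to device. It matters here only because it shows that the times exist as data; the governing text is 3.4.1.5 and 3.4.2.4.

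The primary analysis (SAP 3.4.1.3) is a two-sample t-test on log infarct size, with no covariate and no term for time.

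**The concern.** A median split replaces a duration with two flat categories. A subject who arrived very early counts the same as one just under the median, and two subjects on either side of the median count as different. Three of the nine first-set subgroups are time intervals, so the sponsor evidently wants to know whether the effect on infarct size depends on time. The split answers that question with less precision than the recorded data allow. The cut is also whatever the median of this sample turns out to be, so the two halves do not describe a time window that a later trial could adopt.

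What is at stake is limited to that question: a real time gradient could be missed, or appear as two noisy halves, in a Phase 2b trial meant to inform later development.

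**Working it through.** **Plan figures reproduced first.**

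- Evaluable size: 540 randomized (Protocol 3.1.1) at the 50% exclusion rate (SAP 4) gives 270. 60% of that is 162, as stated. Per arm, 180 × 0.50 = 90, as in Protocol 4.8.2.
- Log SD: the coefficient of variation is redacted, so it is inferred from SAP 4, where 50% predictive power corresponds to an 18% reduction. In the SAP formula, 50% means the observed effect equals 1.96 × the final standard error. So SE = −ln(0.82)/1.96 = 0.1985/1.96 = 0.1013. The original 414 subjects (Protocol 9.2) at 40% exclusion, in three equal groups, give 414 × 0.60/3 = 82.8 per group. Log SD = 0.1013/√(2/82.8) = 0.65.
- Check: with information fraction 0.30, 20% predictive power needs z = 1.96√0.30 − 0.842√0.70 = 0.369. This is a log effect of 0.369 × 0.1013/√0.30 = 0.068, a 6.6% reduction. The SAP says approximately 7%.

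**Information kept by the split.** For a linear relation, efficiency relative to continuous time is the squared correlation between time and its above-median indicator. That correlation is (mean above median − mean below median)/(2 × SD).

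| Assumed time distribution | Correlation | Kept | Lost |
|---|---|---|---|
| Normal (e.g. log time) | √(2/π) = 0.798 | 64% | 36% |
| Uniform | 0.866 | 75% | 25% |
| Exponential | ln 2 = 0.693 | 48% | 52% |
| Lognormal cut at 6 h (median 2–3 h, log SD 0.4–0.8) | simulated | 58–69% | 31–42% |

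At 36% loss, 270 evaluable subjects count as 270 × 0.637 = 172 for this question.

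**Power for the effect-by-time term**, one-sided 0.05. Let b be the assumed change in log treatment effect per SD of log time, and e the efficiency (1 for continuous, 0.637 for split). The standard error is 0.65 × √(1/n₁ + 1/n₂): 0.0839 for 180 vs 90 (regimens pooled) and 0.0969 for 90 vs 90 (one regimen against combined placebo). Power ≈ Φ(b√e/SE − 1.645). For b = 0.20 and 180 vs 90: continuous Φ(2.383 − 1.645) = 77%; split Φ(1.902 − 1.645) = 60%.

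This formula flatters the split slightly, because the time trend left within each half inflates the residual variance. For this case, simulation puts the split between 55% and 58%, depending on how strongly time itself predicts infarct size. The values carried forward are:

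| Gradient b | 180 vs 90: continuous / split | 90 vs 90: continuous / split |
|---|---|---|
| 0.20 | 77% / 58% | 66% / 48% |
| 0.15 | 56% / 40% | 46% / 33% |
| 0.10 | 33% / 24% | 27% / 20% |

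**The case against.** **The gradient may be smaller than the headline case.** This stands. A gradient of 0.20 per SD is as large as the whole 18% effect (−ln 0.82 = 0.198). With a mean log effect of −0.20 it implies a 33% reduction one SD below mean time, none one SD above, and a 22% increase two SDs above. At 0.10 the trial has little power either way, and the split costs 7 to 9 points rather than 18 or 19.

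**The power comparison uses a test that the SAP does not specify.** This also stands: no readable text names an effect-by-time test for these subgroups. The information loss does not depend on a test, and the proposed model supplies the missing term.

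**These are supportive displays, and continuous times stay available for later work.** True, and it limits the weight of the point.

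Four stronger readings are tempting, but the documents do not support them:

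- *The dose rationale makes ischaemic time the key effect modifier.* Protocol 3.2.1 says that a redacted quantity "is expected to increase ~50% in 90 minutes and ~100% in 6 hours", but that is its expected rise after the loading dose, not the duration of ischaemia before treatment. If it bears on any listed interval, it is Dose 1 to pPCI.
- *The entry limit crowds subjects around the cut.* The criterion "Ischemic symptoms for ≤ 6 hours" bounds the range. It says nothing about how times are distributed within it.
- *The plan never uses continuous time.* SAP 3.4.3 (Other Efficacy Analyses) has no readable text and the exploratory material is partly redacted, so the statement holds for the visible text only.
- *The trial's main conclusion is at risk.* The primary test, alpha, sample size and futility rules do not involve these subgroups.

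**Conclusion.** The point holds as an inexpensive improvement to a secondary question. For a roughly linear relation, the median splits in SAP 3.4.1.5 and 3.4.2.4 discard about 36% of the information on whether the effect varies with time; 25% to 52% covers the uniform and exponential cases. If the true relation is a step near the median, little is lost.

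The power figures are illustrative. They rest on an assumed gradient, on planned group sizes (before the switch in Protocol 4.2.1.1 to 1:1 randomization into Cohort B alone), and on a log SD of 0.65 inferred from the original, smaller design. Protocol 9.2 says the sample size was revised in light of the observed blinded variation, so the actual log SD may differ. A larger value lowers power for both methods but leaves the efficiency ratio unchanged.

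**What to change.** In SAP 3.4.1.5 and 3.4.2.4, for each of the three intervals:

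- Add a linear model of log infarct size (or the secondary endpoint on its analysis scale) on arm, continuous log time and arm × log time.
- Report the MEDI6012 versus placebo effect with its confidence interval at the 25th, 50th and 75th percentiles of time, stated in hours so that a later trial can use them.
- Lead with onset-to-door time, because it precedes randomization. The other two intervals end at the device time, after it.
- Add a quadratic term as a check on shape.
- Label the results exploratory, without multiplicity control.
- Keep the above/below-median rows for display.

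The cost is a paragraph of SAP text and a few lines of code, with no new data. The downside is an assumed smooth trend, which the quadratic term and the retained split rows help to check, and a few more exploratory models on overlapping intervals.
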